Evaluation of the Efficacy of Procedural Sedoanalgesia and Infraclavicular Nerve Blockade on Analgesia in Forearm Fractures in the Emergency Department

1. Protocol

Trauma patients constitute a significant portion of emergency department visits. Forearm fractures are common upper extremity fractures in adult patients. A forearm fracture can present as an isolated radius fracture, an isolated ulna fracture, or a double bone radius-ulna fracture. Forearm fractures cause severe pain, both due to the fracture itself and during the reduction process. Pain management is crucial in emergency departments (ED). Therefore, multimodal approaches are available to reduce or eliminate pain during the reduction process. Procedural sedation and analgesia (PSA), which is widely used in emergency departments and effectively reduces pain, is particularly common. However, recent literature suggests the use of peripheral regional block techniques over the use of multiple nonsteroidal anti-inflammatory and/or opioid analgesics for pain palliation.

The aim of our study is to evaluate the success of reduction and pain palliation during the reduction process in patients with forearm fractures using PSA and ultrasound-guided infraclavicular nerve block (ICB). The secondary aim is to compare patient comfort, physician comfort, side effects, length of stay in the emergency department, and the need for pain medication after discharge between these two procedures, and to determine the most appropriate method. With this study, we aim to contribute to practical applications for achieving optimal pain control in patients with forearm fractures in emergency department settings.

PSA (Procedural Sedation and Analgesia) refers to the suppression of a patient's consciousness to maintain vital heart and lung functions while using sedative and dissociative agents combined with analgesics during a medical procedure, with the goal of preventing or minimizing the patient's awareness, response, and memory of the event. However, the use of sedoanalgesic drugs carries significant risks, such as respiratory depression or hypotension, and requires that every patient be monitored and observed at least until they return to a presedation level of alertness. The need for the patient to stay in the emergency department for at least two hours and the requirement for staff to monitor the patient during this time present certain disadvantages, particularly in busy emergency departments. These concerns have led to the exploration of alternative approaches. Ultrasound (US)-guided peripheral nerve blocks are alternatives used in pain management during the reduction of forearm fractures. These techniques are widely used in outpatient settings, orthopedic surgeries, and postoperative pain management in operating rooms. Peripheral nerve blocks involve the use of local anesthetics and are defined as the infiltration of peripheral nerves with local anesthetic agents to reduce motor output and sensory input. Nerve blocks are effective in pain control, act quickly, have low complication rates, and do not require prolonged observation. As a result, the use of peripheral nerve blocks in pain management is increasing in emergency departments.

Patients presenting with forearm fractures to the emergency department will be included in the study. The need for reduction at the time of presentation will be determined by orthopedic doctors. Patients who require reduction and have an ASA classification of ASA 1-2 (ASA: American Society of Anesthesiologists, Table-1) will be included in the study and followed up. The patients will be randomly divided into two groups: Group P, where reduction will be performed under Procedural Sedation and Analgesia (PSA), and Group B, where reduction will be performed under ultrasound-guided infraclavicular nerve block (ICB). Randomization will be done by assigning the first 5 patients to Group P and the next 5 patients to Group B (the procedures are described in detail below), and the following parameters will be evaluated:

Pain levels at the time of arrival, post-procedure but before reduction, and after reduction will be recorded using the Numeric Rating Scale (NRS). (NRS ranges from 0-10, with 0 representing no pain and 10 representing unbearable pain.)

The success of the reduction procedure will be assessed, noting whether additional reduction procedures were required, and the findings on control X-rays after each reduction (radial height, radial inclination, and volar tilt) will be recorded and evaluated by orthopedic doctors. The length of stay in the emergency department will be recorded as the time from the patient's arrival to discharge.

Side effects/complications during the procedures will be recorded.

The need for rescue treatment during the procedure will be evaluated. If the NRS is above 5, the first-line rescue analgesic treatment will be 50 or 100 mg of tramadol IV, administered in 100 cc of normal saline over 15 minutes. If the pain remains above NRS 5, the second-line

treatment will be 50 mcg of fentanyl IV, administered in 100 cc of normal saline over 15 minutes.

The need for pain medication within 24 hours after discharge will be assessed by calling the patients.

Patient satisfaction will be recorded using a 5-point Likert scale (1: very poor, 2: poor, 3: fair, 4: good, 5: very good).

The same satisfaction survey will be administered to the orthopedic doctors who performed the reduction.

Procedures for the groups will be as follows before reduction: The PSA protocol for Group P will be performed by experienced emergency physicians who are skilled in sedation analgesia, advanced life support, and advanced airway management. The patient will be monitored by an experienced doctor or nurse during the sedation period until recovery. Emergency equipment will be readily available in case of any complications. The PSA protocol will include IV ketamine administered at a dose of 1-2 mg/kg. If the NRS remains above 5, additional doses of 0.25-1 mg/kg may be repeated every 5 to 10 minutes as needed. The decision to discharge the patient will be based on the modified Aldrete score, one of the recovery scoring systems.

The ultrasound (US)-guided infraclavicular nerve block protocol for Group B: The infraclavicular block (ICB) is a peripheral nerve block that anesthetizes the brachial plexus at the level of the cords. ICBs are used for anesthesia and/or analgesia during surgical or procedural interventions on the forearm, wrist, hand, and fingers. The block will be applied under ultrasound guidance as follows: The patient will be placed in a supine position, an intravenous (IV) line will be established, and the patient will be monitored. The patient's head will be turned to the side opposite the block site. The arm to be blocked will be adducted and placed in flexion across the patient's chest. After the block site is disinfected with povidoneiodine, a sterile linear ultrasound probe (the LOGIQ P9 ultrasound device currently used in our emergency department) will be placed longitudinally at the recommended site for the infraclavicular block . Once the axillary artery, vein, and the cords of the brachial plexus are visualized, a 22-gauge needle will be advanced in-plane with the ultrasound probe toward the 6-7 o'clock position relative to the artery. The lateral, medial, and posterior cords, containing hypoechoic nerve fascicles ("honeycomb" appearance), will be identified. First, 2 mL of saline will be injected; if the spread is appropriate, the local anesthetic (LA) solution, prepared by diluting 10 mL of 0.5% bupivacaine with 10 mL of normal saline to create 20 mL of 0.25% bupivacaine, will be injected in fractional doses with intermittent negative aspiration. The spread of the local anesthetic within the brachial plexus will be observed as an expanding hypoechoic collection within the plexus. Fifteen minutes after this procedure, the level of anesthesia will be assessed using a cold-hot test, and reduction and casting will be performed

Inclusion Criteria:

Age 18 years and older Diagnosed with a forearm fracture using standard radiography Hemodynamically stable No vascular or nerve injury No infection in the skin or tissues where the needle will pass Able to give written and verbal consent

Exclusion Criteria:

Allergy to drugs used for sedation analgesia and peripheral nerve block Hemodynamically unstable Patients with ASA 3-4 classification (for those in the PSA group) Coagulopathy, liver or kidney failure Patients with opioid, alcohol, or substance abuse Skin infection or open wound at the site where local anesthetic will be applied Pregnant or suspected of being pregnant Those who do not give written and verbal consent

Sample Size: For the planned analyses in this study, the sample size calculation was based on the study by Tekin et al. titled 'Can ultrasound-guided infraclavicular block be an alternative option for forearm reduction in the emergency department? A prospective randomized study.' In that study, a 30% difference between the two groups was found to be significant, and thus, this article was used as a reference for our study. Based on this reference article, with an effect size of 0.5 (medium), an α level of 0.05, and a power of 0.80, it was determined that a total of 78 participants (39 in each group) would be sufficient. The sample size analysis was conducted using the GPower 3.1 program.

Volunteer recruitment for the study will be terminated once the total of 78 patients, as determined by the power analysis, is reached.

The study received approval from the Ankara Etlik City Hospital Ethics Committee on April 24, 2024 (approval code: AEŞH-EK1-2024-0040). However, patient recruitment has not yet started.

Volunteer Recruitment Start: September 1, 2024 [Expected] Primary Completion: June 1, 2025 [Expected] Study Completion: December 1, 2025 [Expected]

2. Statistical analysis

Statistical analysis will be performed using the SPSS 23.0 statistical software package. In the descriptive findings section, categorical variables will be presented as numbers and percentages, while continuous variables will be presented as mean \pm standard deviation for normally distributed data and as median (minimum, maximum) for non-normally distributed data. The normality of the distribution of continuous variables will be assessed using the Kolmogorov-Smirnov test. Comparisons between groups for categorical variables will be evaluated using the chi-square test. For normally distributed quantitative variables, comparisons between the three groups will be made using the ANOVA test. For non-normally distributed quantitative variables, the Kruskal-Wallis test will be used. A p-value of < 0.05 will be considered statistically significant in this study

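### Fracture pattern is pooled, unstratified and unadjusted; if pattern is prognostic, recording it, stratifying on it and adjusting for it would be a cheap improvement

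*Combined protocol and SAP*

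**What the plan says.** Section 1 (Protocol), background: "A forearm fracture can present as an isolated radius fracture, an isolated ulna fracture, or a double bone radius-ulna fracture". The Inclusion Criteria do not restrict or group by pattern; the entry condition is "Diagnosed with a forearm fracture using standard radiography".

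On allocation, section 1 says "Randomization will be done by assigning the first 5 patients to Group P and the next 5 patients to Group B". No stratification factor is named.

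Reduction success belongs to the main aim. On its measurement, section 1 says "The success of the reduction procedure will be assessed, noting whether additional reduction procedures were required", and adds that "the findings on control X-rays after each reduction (radial height, radial inclination, and volar tilt) will be recorded and evaluated by orthopedic doctors". All three listed X-ray measures are radial. Fracture pattern is not among the parameters listed for recording.

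Section 2 (Statistical analysis) says "Comparisons between groups for categorical variables will be evaluated using the chi-square test". Quantitative outcomes get ANOVA, or Kruskal-Wallis if non-normal. No covariate, stratified test or baseline comparison by pattern is planned.

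**The concern.** Pattern is visible on the diagnostic film before allocation, so it is a legitimate baseline factor, and it bears on the first-named outcome. Radial measures cannot describe an isolated ulna fracture in the way they describe a radius fracture, so the mix of patterns in an arm affects what is being measured. It is also plausible that both-bone fractures are harder to reduce.

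If so, an arm that receives more of them will look worse on reduction success, and perhaps on pain, for reasons unrelated to the analgesic method. With 78 patients, the planned analysis could not separate the two. Even with good balance, an unadjusted test ignores whatever variation pattern explains. An adjustment chosen after an imbalance has been seen would be much less credible than one fixed in advance.

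**Working it through.** **Inputs from the plan.** 78 patients, 39 per group; "with an effect size of 0.5 (medium), an α level of 0.05, and a power of 0.80". The plan gives no pattern mix and no success rates by pattern, so every rate below is an assumption.

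**The plan's own figure.** A two-sided t-test at d = 0.5 needs 64 per group for 80% power; at 39 per group power is 58.7%. The 78 is therefore not reproduced from the stated effect size. That is a separate matter, but it means 58.7% is the right starting point in step 5.

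**1. Chance imbalance.** Let q be the both-bone share. With 39 per arm, the difference in shares has SD = √[2q(1-q)/39]. At q = 0.4 this is √(0.48/39) = 0.111, or 11 points. Exact binomial probabilities:

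| q | 15 points or more | 20 points or more |
|---|---|---|
| 0.10 | about 4% | about 0.5% |
| 0.30-0.50 | 17-21% | 6-9% |

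If the overall mix is treated as fixed (hypergeometric), the 30-50% row becomes 13.5-17.4% and 4.6-6.9%.

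**2. Effect on the estimate.** Shift = imbalance × gap in success between patterns. With a 35-point gap (85% vs 50%): 15 × 0.35 = 5.3 points and 20 × 0.35 = 7.0 points. With a 20-point gap: 3.0 and 4.0 points. For comparison, the standard error of the risk difference is about 5-10 points across the scenarios examined.

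**3. Precision, reduction success.** R² = q(1-q)·gap²/[p(1-p)], where p is overall success. With q = 0.3 and 95% vs 75%: p = 0.89 and R² = 0.21 × 0.04/(0.89 × 0.11) = 0.086. The standard error is √(0.0979 × 2/39) = 7.09 points unadjusted and 7.09 × √(1-0.086) = 6.77 adjusted. That is worth 78/(1-0.086) - 78, or about 7 extra patients. Over q = 10-50% and gaps of 10-40 points, R² runs from 0.02 to 0.20 and the gain from about 1 to 19 patients.

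**4. Power, crude chi-square against Cochran-Mantel-Haenszel (simulation, odds ratio 4).**

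| Success, single-bone / both-bone | Both-bone share | Crude | Stratified |
|---|---|---|---|
| 85% / 50% | 40% | 55.2% | 58.5% |
| 80% / 40% | 40% | 61.4% | 65.6% |
| 75% / 55% | 40% | 65.1% | 65.6% |
| 85% / 50% | 10% | 43.4% | 41.6% |
| 90% / 75% | 40% | 40.8% | 37.7% |

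The rates are those of the arm with lower success. With no treatment effect, both tests reject in about 5% of trials. Part of the loss in the last row reflects a slightly higher size for the crude test (5.2% vs 4.8%).

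**5. Power, continuous outcome.** With d = 0.5, 39 per arm and pattern explaining a share R² of the variance, the effective d is 0.5/√(1-R²). At R² = 0.10 this is 0.527 and power is 63%; at R² = 0.15 it is 0.542 and power is 66%. Both compare with 58.7% unadjusted.

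**The case against.** The strongest reply is that nothing in the planned analysis is invalid. Under random allocation, chance imbalance causes no average bias, the crude test keeps its size, and a shift of a few points from a realised imbalance is ordinary sampling variation already counted in the standard error. An unadjusted comparison in a 78-patient, single-hospital trial is a defensible choice. All of this stands.

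A reader might infer that pattern is the main prognostic factor for reduction success. The documents do not say so: the background lists the patterns without stating that they differ in difficulty, pain or success. Displacement, age or delay could matter as much.

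A reader might also infer that adjustment always gains power. Step 4 shows that it can lose a little. Nor should a rise from 80% to 84-86% be quoted for a continuous outcome: that requires d = 0.645, which is not the plan's effect size.

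Finally, the allocation is not random, so balance is not purely a matter of luck. The fixed runs of five are predictable, and a pattern imbalance could also come from selection. That is a larger and separate defect. It does not remove this point, because the plan has no adjustment for pattern with which to address such an imbalance.

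**Conclusion.** The point holds as a conditional, low-cost improvement. It is certain from the text that the patterns are pooled, that allocation is not stratified, that the tests are unadjusted and that the radiographic measures are all radial. It is not established that pattern is prognostic.

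If it is, imbalances of 15 points or more would be fairly common at a both-bone share of 30-50% and uncommon at 10%. With a 35-point success gap, imbalances of 15-20 points move the estimated difference by about 5-7 points. The power consequence for reduction success is small and can go either way, from about +4 to about -3 points. For a continuous outcome it is a gain of roughly 4-7 points if pattern explains 10-15% of variance.

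The documents do not support describing the crude analysis as biased on average or as having an inflated false-positive rate on this account.

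**What to change.** The plan states that recruitment has not started, so the change can be made before the first patient.

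- Record fracture pattern (all three types) at baseline from the diagnostic film, before allocation.
- When the 5/5 runs are replaced by concealed random permuted blocks, stratify by both-bone versus single-bone. Two strata avoid sparse cells; report isolated ulna fractures descriptively, since the radial measures fit them least.
- Pre-specify a pattern-adjusted comparison (Mantel-Haenszel or a standardised risk difference) for reduction success and repeat reduction, with the crude chi-square as sensitivity analysis. This needs a written definition of success, which the plan does not yet give. Avoid logistic models with many terms, because failures may be few.
- Include pattern, with arrival NRS, in the model for pain.

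The cost is two allocation lists instead of one, one extra recorded item, and a possible loss of about 2 to 3 points of power for reduction success if both-bone fractures prove rare or success very high.

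### The allocation rule (five patients to PSA, then five to block, in order of enrolment) is not random, and every assignment is known in advance

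*Combined protocol and SAP*

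**What the plan says.** The group-allocation paragraph of Section 1 (Protocol) first states the intent: "The patients will be randomly divided into two groups". It then gives the method: "Randomization will be done by assigning the first 5 patients to Group P and the next 5 patients to Group B". Nothing else is said about how the sequence is produced, who holds it, or when the arm is revealed.

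Other text that bears on the point:

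- Entry depends on a clinical judgement: "The need for reduction at the time of presentation will be determined by orthopedic doctors".
- The Sample Size paragraph concludes that "a total of 78 participants (39 in each group) would be sufficient".
- Pain (NRS) and satisfaction are rated by the patient, and the doctors who perform the reduction also rate satisfaction. Orthopaedic doctors evaluate the control X-rays. No masking of any assessor is described.
- Section 2 (Statistical analysis) lists unadjusted group comparisons only, with no term for calendar period or run of five.
- The ethics approval paragraph states that "patient recruitment has not yet started".

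**The concern.** The stated method contradicts the stated intent. A rule that reads the arm off the order of enrolment contains no chance element, so the comparison lacks the basis on which its p-values would be interpreted, and it would be wrong to report the trial as randomised.

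Three features make this more than a matter of wording.

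1. **Foreknowledge.** Whoever judges eligibility or seeks consent can know the next arm. A patient who seems anxious, in severe pain or hard to reduce can be left out, or approached differently, depending on whose turn it is.
2. **Exposed outcomes.** Patients and operators will know whether ketamine sedation or a needle block was used. NRS and satisfaction are subjective. Concealed random allocation is the main protection available, and it is absent.
3. **Clustering in time.** Each arm is treated in unbroken runs of five, so short-term changes in caseload or working practice fall on one arm at a time.

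A related wording conflict should be reconciled. The allocation paragraph restricts all patients to ASA 1-2, while the exclusion list has "Patients with ASA 3-4 classification (for those in the PSA group"). The conflict is a separate matter, but an exclusion that can be read as applying to one arm is more easily applied selectively when the arm is known beforehand.

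**Working it through.** **Inputs from the document:** runs of 5; total 78, 39 per group; expected recruitment start 1 September 2024 and primary completion 1 June 2025 (273 days). **Assumptions:** the 5/5 pattern repeats (not stated, but otherwise the rule covers only 10 patients); recruitment is even and ends at primary completion. The bias sizes and within-run correlations below are also assumed, because the document gives none.

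**1. The plan's own split.** Seven full cycles of 5 + 5 use 70 patients (35 and 35). The last 8 are 5 to Group P and 3 to Group B, giving 40 and 38 rather than 39 and 39. The effect on precision is negligible: √(40 × 38/78) = 4.414 against √(39/2) = 4.416.

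**2. Predictability.** The rule allows one sequence, so 78/78 = 100% of assignments are known. Simple randomisation gives 50%. For permuted blocks, suppose a person has seen all past assignments and always guesses the arm that is behind. The expected number of correct guesses in a block of 2m is m + 2^(2m−1)/C(2m, m) − 1/2:

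- block of 4: 2 + 8/6 − 0.5 = 2.83
- block of 6: 3 + 32/20 − 0.5 = 4.10
- block of 8: 4 + 128/70 − 0.5 = 5.33

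A random mix of 4 and 6 gives (2.83 + 4.10)/10 = 69%. A mix of 4, 6 and 8 gives (2.83 + 4.10 + 5.33)/18 = 68%, which agrees with a simulation over 78 patients (68%).

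**3. Effect of selection on the error rate.** Let b be the between-arm bias in SD units when there is no true difference. The test statistic then has mean b√(39/2) = 4.416b, and the type I error is P(|Z + 4.416b| > 1.96).

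| Shift in each arm, opposite directions (SD) | b (SD) | Mean of Z | Type I error |
|---|---|---|---|
| 0 | 0 | 0 | 5% |
| 0.05 | 0.1 | 0.44 | 7.3% |
| 0.1 | 0.2 | 0.88 | 14.3% |
| 0.2 | 0.4 | 1.77 | 42.3% |

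**4. Time structure.** 273/78 = 3.5 days per patient, so a run of five lasts 5 × 3.5 = 17.5 days. 78/5 = 15.6, so there are 16 runs, the last incomplete.

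- *Slow trend.* Group P has eight runs with mean positions 3, 13, …, 73, averaging 38.0. Group B has 35 patients averaging 38 and three averaging 77: (35 × 38 + 3 × 77)/38 = 41.1. The arms differ by about 3 enrolment positions, so a steady linear drift nearly cancels.
- *Short-term variation.* If outcomes within a run have correlation ρ, the design effect is 1 + (5 − 1)ρ and the type I error is 2[1 − Φ(1.96/√DE)]. At ρ = 0.05, DE = 1.2 and the error is 7.4%. At ρ = 0.01 (DE 1.04) it is about 5.5%, and at ρ = 0.10 (DE 1.4) about 10%.

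**The case against.** The strongest reply accepts that the rule is not random but says its consequences are overstated.

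- **Repetition is inferred.** This is correct, and it is labelled as an assumption above. No other natural reading reaches 78.
- **The 40/38 split is trivial.** It is. Varying blocks stopped at 78 can also end unequal. It carries no weight here.
- **Time-period bias is small.** This is largely right for slow trends. The document gives no staff rota, and 17.5 days would probably span many shifts, so no claim about particular teams can be made. Short-term variation remains possible.
- **The bias sizes are invented.** They are assumptions, and at the low end the error rate rises only to about 7%. They show what bias would do, not that it will occur.
- **Some protection is possible.** Assessors unaware of the arm could read the X-rays and make the 24-hour telephone call, and adjustment for arrival NRS could remove part of an imbalance. Neither is planned, and neither reaches unrecorded choices about whom to enrol.
- **Steering is difficult with an acute fracture.** Deferring such a patient is hard, but not enrolling one is easy. This narrows the risk without removing it.

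None of these points supplies a chance element or conceals the next assignment.

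**Conclusion.** The concern holds and must be fixed before the first patient is enrolled. As written, allocation is deterministic, fully predictable (100% of assignments, given repetition of the pattern) and unconcealed, so the study is at best quasi-randomised. That conclusion follows from the text and needs none of the assumed bias values. Selection at enrolment is the main risk; clustering in time is secondary. The possible inflation of the 5% error rate ranges from about 7% to 42% for between-arm biases of 0.1 to 0.4 SD, and is about 7% for a within-run correlation of 0.05. These figures are illustrative. Analysis could correct part of any bias through recorded baseline variables, but not reliably all of it. The derivation of the sample size is a separate question and does not affect this finding.

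**What to change.** Replace the allocation sentence with wording such as: *Patients will be allocated 1:1 from a computer-generated list in permuted blocks of randomly varying size (for example 4 and 6). The list will be prepared by a person not involved in enrolment and held in sequentially numbered, opaque, sealed envelopes. Each envelope will be opened only after eligibility is confirmed and consent is signed.*

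Block sizes should not be disclosed to enrolling staff. Treatment is visible, so a person tracking past assignments could still guess better than chance (about 69% with blocks of 4 and 6), but no longer with certainty. A mix of 4, 6 and 8 is marginally better.

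The cost is one protocol sentence, a list, 78 envelopes and at most a routine amendment, since ethics approval is dated 24 April 2024. Sample size, treatments and follow-up are unchanged.

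The statement that recruitment has not begun is undated and stands beside an expected start of 1 September 2024, so confirm that it is still true. If patients have already been allocated by the 5/5 rule, identify them, describe that part of the study as quasi-randomised, and do not report them as randomised.

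### The radiographic measures of reduction are scheduled only after reduction, with no reading of the diagnostic film that every patient has and no baseline adjustment

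*Combined protocol and SAP*

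**What the plan says.** Section 1 (Protocol) puts reduction in the main aim, beside pain: "The aim of our study is to evaluate the success of reduction and pain palliation during the reduction process". The outcome list then gives reduction success two components. One is a count, "noting whether additional reduction procedures were required". The other is radiographic: "the findings on control X-rays after each reduction (radial height, radial inclination, and volar tilt) will be recorded and evaluated by orthopedic doctors". No part of the document schedules these three values, or any grade of displacement, before reduction.

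A pre-reduction film nevertheless exists for everyone, because the inclusion criteria require "Diagnosed with a forearm fracture using standard radiography". Pain does get a starting value: "Pain levels at the time of arrival, post-procedure but before reduction, and after reduction will be recorded".

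On allocation, section 1 states "Randomization will be done by assigning the first 5 patients to Group P and the next 5 patients to Group B". Section 2 (Statistical analysis) compares continuous variables by ANOVA or Kruskal-Wallis. It mentions no covariate and no change from baseline.

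**The concern.** Where a fracture ends up after manipulation plausibly depends in part on how displaced it was beforehand. If starting displacement is neither recorded nor used, three things are lost:

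- the variance it would explain in an outcome named in the main aim;
- the ability to show that the arms were comparable on the most obvious prognostic factor for that outcome;
- the ability to report the correction achieved as well as the final position.

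The second loss matters more here than in a trial with concealed random allocation. Under fixed runs of five, anyone who knows the sequence can tell which arm the next patient will join. Entry also depends on a clinical judgement: "The need for reduction at the time of presentation will be determined by orthopedic doctors". Comparability in starting displacement therefore cannot be taken from the allocation method and would have to be shown from data.

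**Working it through.** **Inputs.** 39 per arm comes from the Sample Size paragraph. The documents give no pre/post correlation r for the radiographic values, so r is assumed over a range that includes low values. Reduction aims at alignment whatever the starting position, so r may be small. The plan states no figure of its own on this point, so there is none to reproduce. The sample size is used only as the number per arm.

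**1. Chance imbalance under random allocation.** In SD units, the standard error of the between-arm difference in a baseline value is √(2/n).

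- n = 39: √(2/39) = 0.226. P(|difference| > 0.3 SD) = 2 × P(Z > 0.3/0.226) = 2 × P(Z > 1.325) = 0.185, about 19%.
- n = 30 (assumed): √(2/30) = 0.258. 2 × P(Z > 1.162) = 0.245, about 25%.

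The second line is there because all three measures belong to the radius, while section 1 counts isolated ulna fractures as forearm fractures. The number per arm with usable values may be below 39, by an amount the documents do not state.

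**2. What such an imbalance does.** An unadjusted comparison of post-reduction values moves by about r × imbalance. For 0.3 SD this is 0.03 SD at r = 0.1, 0.06 at 0.2, 0.09 at 0.3 and 0.15 at 0.5. The largest of these is 0.15/0.226 = 0.66 of one standard error.

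**3. Precision.** Adjusting for the baseline multiplies residual variance by 1 − r². The equivalent gain in patients is 1/(1 − r²).

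| r (assumed) | variance removed | equivalent gain in patients |
|---|---|---|
| 0.1 | 1% | 1/0.99 = 1.01 |
| 0.2 | 4% | 1/0.96 = 1.04 |
| 0.3 | 9% | 1/0.91 = 1.10 |
| 0.5 | 25% | 1/0.75 = 1.33 |

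Estimating the slope costs a variance factor of about 1 + 1/(78 − 4) = 1.014. At r = 0.1 the net factor is 0.99 × 1.014 = 1.00, so nothing is gained.

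**4. The same in terms of power.** For a true difference of 0.5 SD, 39 per arm, two-sided α = 0.05 and the normal approximation, power = Φ(0.5/(0.226 × √(1 − r²)) − 1.96). This gives 0.60 at r = 0, 0.64 at r = 0.3 and 0.72 at r = 0.5.

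**5. Systematic imbalance.** No figure can be put on this from the documents. Steps 1 and 2 assume random allocation, so 19% describes chance alone and does not bound what predictable allocation could produce.

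**The case against.** The strongest reply has four parts.

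- **Randomisation makes a baseline unnecessary.** Under true randomisation an unadjusted post-reduction comparison is unbiased, and chance imbalance is already in its standard error and p-value. This stands. A reader might infer that the trial cannot tell a better reduction from a less displaced fracture, or that a chance imbalance would be wrongly credited to one arm. Neither follows from chance imbalance: what it costs is precision. The reply is weaker here because fixed runs of five are not random allocation.
- **Reduction success is not only radiographic.** This also stands. A reader might infer that reduction success as a whole lacks a baseline, but the need for a repeat reduction can be counted without one. Final alignment is also a legitimate endpoint in its own right, and section 1 never says that the trial asks about correction achieved. That no threshold on the three measures defines success is a separate gap, which a baseline would not close.
- **The information is not lost.** The protocol is silent on pre-reduction values and does not exclude them. They could be read later if the films are kept. What is missing is a planned reading and a planned adjustment. A later reading would be unplanned, possibly by readers who know the result.
- **The precision gain may be small.** This is true if r is low, as the table shows.

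**Conclusion.** The point holds for the radiographic component of reduction success. The three values are scheduled only on control films, although a diagnostic film exists for every patient, and they are compared without adjustment. The timing and the lack of adjustment are plain in the text.

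The size is less certain. The precision gain runs from nothing worthwhile at r = 0.1 to a 25% cut in residual variance at r = 0.5, and every r is an assumption. The 19% probability of a chance imbalance above 0.3 SD assumes random allocation and 39 measurable patients per arm. It rises to about 25% at an assumed 30.

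The stronger argument is comparability. With predictable allocation, a systematic difference in starting displacement is possible, and the plan schedules nothing that would show it. The documents give no evidence that such a difference will occur. This is a worthwhile and cheap improvement, and its absence does not invalidate the trial.

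**What to change.** Add to the outcome list: 'For fractures involving the radius, radial height, radial inclination and volar tilt will also be measured on the diagnostic radiograph, by the same method as on the control films.' A reader unaware of the arm is preferable. The plan should also say how isolated ulna fractures enter this outcome.

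Add to section 2:

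- Name one control film for the comparison, since films are taken after each reduction and a patient may have several. One choice is the first post-reduction film, with the final film reported as well.
- Compare the values between arms by a linear model adjusted for the matching diagnostic value.
- Report the diagnostic values by arm, and the correction achieved beside the final position.

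The cost is three extra readings per patient on a film already taken, with no additional film, visit or staff. The drawback is that the precision gain may be small if r is low, although the check on comparability remains useful. The document states that recruitment had not begun, so on its own terms the change can cover every patient. Adjustment would show and partly correct an imbalance in starting displacement. It would not make the allocation random, and that needs its own remedy.
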